**Table 7: Nonhematologic Toxicities Leading to Dose Hold, Modification, or Discontinuation of SRF617**

| Toxicity   | Recommended dose delay or reduction   |
|--|---|
| Immune-mediated AEs   |   |
| Grade 2 or Grade 3 immune-mediated AEs   | Hold SRF617 until resolves to Grade $\leq$ 1 and resume with dose reduced by 1 level.   |
| Grade 4 immune-mediated AEs  | Permanently discontinue SRF617.   |
| Hepatotoxicity  |   |
| $> 2 \times$ ULN bilirubin AND Grade $\geq$ 2 ALT/AST ( $> 3 \times$ ULN) in patients who enroll with Grade $\leq$ 1 ALT/AST | In the absence of biliary obstruction or other cause responsible for the concurrent elevation, permanently discontinue SRF617.  |
| OR   |   |
| $> 2 \times$ ULN bilirubin AND doubling of ALT/AST in patients who enroll with Grade 2 ALT/AST                               |   |
| Grade 4 ALT/AST elevation  | Permanently discontinue SRF617.   |
| OR   |   |
| Grade 4 bilirubin elevation  |   |
| Metabolic   |   |
| Grade 3 electrolyte disturbance  | Hold SRF617 until resolves to Grade $\leq$ 1 or Baseline and resume with same dose (first occurrence) or with dose reduced by 1 level after resolution (second occurrence).   |
| Grade 4 electrolyte disturbance  | Hold SRF617 until resolves to Grade $\leq$ 1 or Baseline and resume with same dose if resolves in $\leq$ 72 hours; permanently discontinue if resolution takes $>$ 72 hours.  |
| Gastrointestinal  |   |
| Grade 3 vomiting, diarrhea, or nausea  | Hold SRF617 until resolves to Grade $\leq$ 1 or Baseline and resume with same dose if resolves in $\leq$ 72 hours with supportive care. If it lasts $>$ 72 hours despite optimal supportive care, resume with dose reduced by 1 level.
Patients must be contacted by the Investigator or trial nurse daily until it is clear that the problem has resolved or requires additional support (eg, hospitalization). |
| Grade 4 vomiting or diarrhea   | Permanently discontinue SRF617.   |

| Toxicity  | Recommended dose delay or reduction  |
|---|--|
| Other nonhematologic toxicities  |  |
| Grade 2 or Grade 3 AEs that, in the opinion of the Investigator, require dose reduction   | Hold SRF617 until resolves to Grade $\leq$ 1 or Baseline and resume with dose reduced by 1 level.
Evaluate at least once weekly after the initial identification of the toxicity until its resolution or stabilization. |

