|   | Grade 2   | Consider etrumadenant dose modification as clinically indicated; otherwise continue at the same dose.

For suspected etrumadenant-related events: 
 
Immediately institute supportive measures.
 
If the event does not resolve to Grade 1 or better within 7 days, consider dose interruption. If event resolves to Grade 1 or better, resume etrumadenant at the same dose or with a one-level dose reduction (Table 9).
 
Etrumadenant dose re-escalation is permitted at the Investigator's discretion.
 
 |  |
|   | Grade 3   | Withhold etrumadenant for at least 7 days until toxicity resolves to Grade 1 or better.

For suspected etrumadenant-related events: 
 
Immediately institute supportive measures.
 
If event resolves to Grade 1 or better within 56 days, resume etrumadenant with a one-level dose reduction (Table 9).a If not, permanently discontinue etrumadenant and contact Medical Monitor.
 
  |  |

| Event   | Severity  | Etrumadenant action to be taken  | Zimberelimab action to be taken  |
|---|---|--|--|
|   |   | 
 
Etrumadenant dose re-escalation is permitted at the Investigator's discretion.
 
   |  |
|   | Grade 4  | Permanently discontinue etrumadenant and contact Medical Monitor   | Permanently discontinue zimberelimab and contact Medical Monitor   |
| Hepatic toxicity
(including elevations in transaminases and/or bilirubin) | Grade 1-2
ALT/AST $\leq 5 \times$ ULN                     | Continue etrumadenant at the same dose level at the Investigator's discretion. Monitor LFTs more frequently until return to $< 3 \times$ ULN or Baseline.  | Refer to the NCCN or institutional guidelines for the Management of Immune CPI-Related Toxicities for symptom-directed supportive care. Zimberelimab, if interrupted, may be withheld for up to 56 days after event onset. |

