|   | Grade 3
ALT/AST $> 5 \times$ ULN but $\leq 20 \times$ ULN | 
For suspected non-immune-mediated transaminase elevations:
 
 
Withhold etrumadenant and zimberelimab for up to 56 days.
 
Monitor LFTs at least weekly for a minimum of 4 weeks until transaminases return to <math>< 3 \times</math> ULN or Baseline.
 
Consider patient referral to GI specialist for evaluation and liver biopsy to establish etiology of hepatic injury.
 
If event resolves to Grade 1 or better within 56 days, resume etrumadenant with a one-level dose reduction (Table 9) and resume zimberelimab.a If not, permanently discontinue etrumadenant and zimberelimab and contact Medical Monitor.
 
 
For suspected immune-mediated transaminase elevations:
 
 
Permanently discontinue zimberelimab and contact Medical Monitor.
 
Withhold etrumadenant for up to 56 days.
 
Consider patient referral to GI specialist for evaluation and liver biopsy to establish etiology of hepatic injury.
 
Initiate treatment with corticosteroids equivalent to 1-2 mg/kg/day oral prednisone. If event does not improve within 48 hours after initiating corticosteroids, consider adding an immunosuppressive agent.
 
If event resolves to Grade 1 or better within 56 days, taper corticosteroids over <math>\geq 1</math> month and resume etrumadenant with a one-level dose reduction (Table 9).a If not, permanently discontinue etrumadenant and contact Medical Monitor.
 
 |  |
|   | Grade 4
ALT/AST $> 20 \times$ ULN                         | Permanently discontinue etrumadenant and contact Medical Monitor. For suspected immune-mediated transaminase elevations, follow Grade 3 management guidelines.   | Permanently discontinue zimberelimab and contact Medical Monitor. For suspected immune-mediated transaminase elevations, follow Grade 3 management guidelines.   |
|   | ALT/AST $> 3 \times$ ULN with                                       | 
 
Permanently discontinue etrumadenant and zimberelimab and contact Medical Monitor.
 
Monitor liver function at least weekly until values return to Baseline.
 
  |  |

| Event  | Severity                       | Etrumadenant action to be taken   | Zimberelimab action to be taken  |

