|  | Grade 2                        | 
 
Consider etrumadenant dose modification as clinically indicated, otherwise continue at the same dose.
 
Initiate symptomatic treatment.
 
Referral to GI specialist is recommended.
 
For recurrent events or events that persist > 5 days, initiate treatment with corticosteroids equivalent to 1-2 mg/kg/day oral prednisone.
 
1st occurrence: If etrumadenant was withheld and event resolves to Grade 1 or better within 56 days, resume etrumadenant at the same dose level.
 
Recurrent or persistent events: If etrumadenant was withheld and event resolves to Grade 1 or better within 56 days, resume etrumadenant with a one-level dose reduction (Table 9).a If not, permanently discontinue etrumadenant and contact Medical Monitor.
 
 |  |

| Event  | Severity         | Etrumadenant action to be taken   | Zimberelimab action to be taken                         |
|--|------------------|---|---|
|  |                  | 
 
Etrumadenant dose re-escalation is permitted at the Investigator's discretion.
 
  |   |
|  | Grade 3   | 
Withhold etrumadenant for up to 56 days after event onset.
 
For suspected immune-mediated events (including colitis):
 
 
Refer patient to GI specialist for evaluation and confirmatory biopsy.
 
Initiate treatment with corticosteroids equivalent to 1-2 mg/kg/day IV methylprednisolone and convert to 1-2 mg/kg/day oral prednisone or equivalent upon improvement.
 
Follow guidance for Grade 2 recurrent or persistent events.
 
   |   |
|  | Grade 4   | 
Permanently discontinue etrumadenant and zimberelimab and contact Medical Monitor.
 
 
Refer patient to GI specialist for evaluation and confirmation biopsy.
 
Initiate treatment with corticosteroids equivalent to 1-2 mg/kg/day IV methylprednisolone and convert to 1-2 mg/kg/day oral prednisone or equivalent upon improvement. If event does not improve within 48 hours after initiating corticosteroids, consider adding an immunosuppressive agent.
 
If event resolves to Grade 1 or better, taper corticosteroids over <math>\geq</math> 1 month.
 
 |   |

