Abbreviations: ALT = alanine aminotransferase; AST = aspartate aminotransferase; CPI = checkpoint inhibitor; GI = gastrointestinal; IV = intravenous; LFT = liver function test; NCCN = National Comprehensive Cancer Network; ULN = upper limit of normal

a The dose of etrumadenant can be reduced from 150 mg to 100 mg (ie, one dose level) and then from 100 mg to 75 mg for management of drug-related toxicities. Additional dose reductions are not allowed. If a dose reduction is indicated for a patient receiving the 75 mg dose of etrumadenant, then that patient should discontinue etrumadenant.

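### Table 10's Grade 4 hepatic cell stops etrumadenant permanently, then refers suspected immune-mediated cases to Grade 3 guidance that restarts it

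*Protocol*

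**What the plan says.** Protocol Table 10 (Section 7.4.1.2) sets management of events related to etrumadenant or zimberelimab. Its Grade 4 hepatic row covers ALT/AST above 20 x ULN.

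- Etrumadenant cell: "Permanently discontinue etrumadenant and contact Medical Monitor. For suspected immune-mediated transaminase elevations, follow Grade 3 management guidelines".
- Zimberelimab cell: "Permanently discontinue zimberelimab and contact Medical Monitor. For suspected immune-mediated transaminase elevations, follow Grade 3 management guidelines".

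The Grade 3 hepatic row has a separate block for suspected immune-mediated elevations. It stops zimberelimab permanently. For etrumadenant it says "Withhold etrumadenant for up to 56 days", asks sites to consider referral to a GI specialist and liver biopsy, starts corticosteroids, and suggests adding an immunosuppressant if there is no improvement in 48 hours. If the event reaches Grade 1 or better within 56 days, steroids are tapered and the site is to "resume etrumadenant with a one-level dose reduction". Otherwise it is to "permanently discontinue etrumadenant and contact Medical Monitor".

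A further hepatic row covers ALT/AST above 3 x ULN with bilirubin above 2 x ULN: "Permanently discontinue etrumadenant and zimberelimab and contact Medical Monitor". Patients with Gilbert syndrome are exempt and go back to the row for their ALT/AST level. Footnote a adds: "If a dose reduction is indicated for a patient receiving the 75 mg dose of etrumadenant, then that patient should discontinue etrumadenant".

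**The concern.** A site managing a suspected immune-mediated Grade 4 transaminase rise gets two incompatible end states for etrumadenant from one cell: never again, or back on at a lower dose once the liver tests recover. Whether to re-expose a patient after ALT/AST above 20 x ULN is a safety decision that the table should settle beforehand.

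A restart would also reach several descriptive summaries in the SAP: etrumadenant disposition (6.2), exposure (8.1), the end of the treatment period (5.1), possibly the TEAE window (11.1), and whether an event is counted as leading to withdrawal or to interruption and dose reduction.

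**Working it through.** The plan states no figure to reproduce on this point. The check is a comparison of texts, with a little arithmetic for size.

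**1. Follow both sentences of the etrumadenant cell** for a suspected immune-mediated Grade 4 rise without bilirubin above 2 x ULN.

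| Path | Zimberelimab | Etrumadenant |
|---|---|---|
| First sentence | permanent stop | permanent stop |
| Second sentence, via the Grade 3 immune-mediated block | permanent stop | hold up to 56 days, then resume one level lower if recovered |

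The paths agree for zimberelimab and conflict for etrumadenant.

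**2. Look for text elsewhere that cancels the resume step.**
- Section 4.7 and the opening of Section 7.4 deal with discontinuation and with continuing the remaining drugs. Neither mentions Grade 4 hepatic rechallenge.
- Section 7.4.1.2 caps a hold at 56 days and allows two reductions. It bars nothing at Grade 4.
- Footnote a limits the number of reductions only.
- The concurrent-bilirubin row covers only patients with that bilirubin rise.
- Table 7 lists "Grade 4 ALT/AST elevation" as a reason for permanent discontinuation, but of SRF617 only.

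No text outside the cell cancels it.

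**3. Ask whether a cross-reference in this table can carry a restart.** It can. The Grade 3 gastrointestinal row has no resume step of its own. It points immune-mediated events to the guidance for recurrent or persistent Grade 2 events, and that is where the reduced-dose restart is found.

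**4. Compare the other Table 10 rows that include Grade 4.**

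| Row | Etrumadenant |
|---|---|
| Dermatologic, Grade 4 | permanent stop, no restart |
| Gastrointestinal, Grade 4 | permanent stop; referral, steroids and taper written out; no restart |
| Other etrumadenant-related, Grade 4 | permanent stop, no restart |
| Other zimberelimab-related, Grade 4 | permanent stop, no restart |
| Infusion-related reaction, Grade 3-4 | consider modification, otherwise continue |
| Fatigue, Grade 3-4 | consider modification, otherwise continue |

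All four rows specific to Grade 4 stop etrumadenant; the two combined rows do not. Where the table does want a restart after a Grade 4 event, it sets a condition: in the other etrumadenant-related row, zimberelimab may resume if the event improves and the Medical Monitor agrees.

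**5. Size if the second sentence were followed literally.** Planned etrumadenant dose (SAP 8.1): 150 x 28 = 4,200 mg per cycle.
- From 150 mg: 100 x 28 = 2,800 mg; 2,800/4,200 = 66.7%.
- From 100 mg: 75 x 28 = 2,100 mg; 2,100/4,200 = 50.0%.
- From 75 mg: discontinue under footnote a, so there is no conflict.

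These are ratios for a full cycle after restart. They are not the patient's relative dose intensity under SAP 8.1, which divides cumulative dose by cycles initiated and so mixes cycles before and after the event.

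**6. TEAE window.** Assume SRF617 and zimberelimab stop at the event and no new anticancer therapy starts. The window then ends at the later of last etrumadenant + 30 days and last zimberelimab + 90 days. A restart moves it only if the last etrumadenant dose falls more than 90 - 30 = 60 days after the last zimberelimab dose.

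**The case against.** The strongest reply is that the cell already answers the question. Its first sentence ends etrumadenant permanently, and elsewhere Table 10 uses withholding for holds that may end in a restart and permanent discontinuation for stops. On that view the second sentence brings in only work-up and steroids, as it must in the zimberelimab cell. This stands as the better reading. It does not remove the conflict, because the cross-reference is unrestricted and the table uses a cross-reference elsewhere to reach a restart.

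A second reply is that the second sentence could be a deliberate exception for immune-mediated cases. The Grade 4 row for other zimberelimab-related toxicity, which also stops etrumadenant, weakens that idea but does not rule it out. The fix should therefore leave the sponsor room to state a different intent.

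A third reply is that the practical effect is slight, and this stands. The cell requires Medical Monitor contact. With zimberelimab stopped and SRF617 normally stopped under Table 7, continuing etrumadenant alone would ordinarily need clinical benefit and the agreement of Investigator and Sponsor (Section 4.7). Divergent restarts are unlikely.

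A reader might infer more than the documents support:
- That nothing in the protocol excludes a restart. The cell's own first sentence does.
- That Table 10 stops etrumadenant at every Grade 4 event. The infusion-reaction and fatigue rows show otherwise.
- That the zimberelimab cell has the same fault. Both of its paths end in a permanent stop.
- That relative dose intensity would be 66.7% or 50.0% instead of zero. After a permanent stop, counting cycles for each drug received, no further etrumadenant cycle is started, so no zero enters the SAP calculation.

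**Conclusion.** The concern holds as an internal contradiction in one toxicity-management cell. For suspected immune-mediated ALT/AST above 20 x ULN, the etrumadenant instruction is both a permanent stop and, by unrestricted cross-reference, a hold with a possible reduced-dose restart. Permanent stop is the better-supported reading, but the text does not settle it.

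The affected group is narrow. The patient must recover to Grade 1 or better within 56 days, be on 150 or 100 mg, fall outside the concurrent-bilirubin row (unless exempt for Gilbert syndrome) and ordinarily still be benefiting. SAP Section 2 reports 15 treated and no further enrollment, with those already enrolled or consented allowed to continue under the protocol, so the rule matters only for anyone still on etrumadenant. The documents give no rate for this event, so no probability is stated.

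Sample size, error rates and the primary endpoint definition are unaffected. The point is worth correcting because it concerns rechallenge after severe liver injury and the correction is small.

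**What to change.** In the Grade 4 hepatic etrumadenant cell of Table 10, keep the cross-reference and add to its end: 'except that etrumadenant must not be resumed.' Keeping the cross-reference matters: GI referral, liver biopsy, corticosteroids, the added immunosuppressant if there is no improvement in 48 hours, and the taper all remain in force. A replacement sentence listing only some of these could be read as dropping the rest for the sickest patients.

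If the sponsor did intend rechallenge, the cell should instead say so explicitly and require Medical Monitor agreement.

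The zimberelimab cell needs no change. The cost is one clause in one cell, with no new data collection and no change to the analysis methods.

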## **7.5. Drug Accountability**

The Investigator or designee is responsible for taking an inventory of each shipment of study drug received and comparing it with the accompanying drug order form.

All unused study drug will be retained at the site. After full drug accountability and reconciliation, the Investigator will dispose of any study drug at the clinical trial site per site procedures, or if necessary, all study drug will be returned to the Sponsor, or its designee. Disposition of all study drug should be documented, including any study drug that is lost or damaged.

## **7.6. Assignment to Treatment**

All patients will receive open-label study drug at a dose and schedule based on the trial design (see Section 4).

## 8. SAFETY DATA COLLECTION, RECORDING, AND REPORTING

### 8.1. Adverse Events

#### 8.1.1. Definition of an Adverse Event

An AE is defined as any untoward medical occurrence associated with the use of a drug, or with trial participation, whether or not considered related to study drug.

An AE can therefore be any unfavorable and unintended sign (including an abnormal laboratory finding, for example), symptom, or disease temporally associated with the use of the medicinal product, whether or not considered related to the medicinal product.

AEs include worsening of a preexisting medical condition as well as clinically significant changes from Baseline laboratory values/conditions. Worsening of the preexisting medical condition (eg, diabetes, hypertension) means that it has increased in severity, frequency, and/or duration, and/or has an association with a significantly worse outcome. A preexisting condition that has not worsened during the trial is not considered an AE. Progression of the cancer under study is not considered an adverse event unless it results in hospitalization or death.

#### 8.1.2. Definition of Serious Adverse Event

An AE or suspected adverse reaction is termed “serious” if according to the Investigator or Sponsor, it:

- Results in death
- Is life-threatening
- Requires inpatient hospitalization or prolongation of existing hospitalization
  - Elective or preplanned treatment for a preexisting condition that is unrelated to the indication under study and has not worsened since signing the ICF (as documented as medical history on the eCRF) is not considered an SAE.
  - Scheduled therapy for the target disease of the trial, including admissions for transfusion support or convenience, is not considered an SAE.
- Results in persistent or significant disability/incapacity or substantial disruption of the ability to conduct normal life functions
- Results in congenital anomaly/birth defect
- Is considered an important medical event
  - If an AE does not meet one of the serious criteria, but the Investigator or Sponsor considers an event to be clinically important, the event could be classified as an SAE under the criterion of important medical event. Examples of such medical events may include allergic bronchospasm requiring intensive treatment in an emergency room or at home, or blood dyscrasias or convulsions that do not result in inpatient hospitalization.

Per NCI-CTCAE version 5.0, if death is due to an AE (eg, Cardiac disorders: Cardiac arrest; infection, pulmonary embolism), it should be reported as a Grade 5 event under that System Organ Class and Preferred Term. However, if death is due to disease progression but cannot be attributed to a specific NCI-CTCAE term associated with Grade 5, the AE should be reported as NCI-CTCAE Preferred Term “disease progression” found in the System Organ Class, “General disorders and administration site conditions.” Evidence that the death was a manifestation of the underlying disease (eg, radiological changes suggesting tumor growth or progression; clinical deterioration associated with a disease process) should be submitted.

### **8.1.3. Definition of an Adverse Event of Special Interest**

AESIs will be collected to evaluate potential class effects for antibodies targeting CD39. AESIs for this trial are defined as thromboembolic events, eg, DVT, pulmonary embolism, stroke, myocardial infarction.

## **8.2. Procedures for Recording and Reporting Adverse Events**

### **8.2.1. Recording Adverse Events**

Patients will be instructed to report all AEs and will be asked a general health status question at each trial visit. All SAEs occurring in patients will be recorded in the eCRF from the time of signing the ICF through the Safety Follow-up visit, 30 days after the last dose of SRF617, 30 days after the last dose of etrumadenant, or 90 days after the last dose of zimberelimab (30 days after the last dose of zimberelimab if the patient starts another anticancer therapy), whichever is later. All AEs occurring in treated patients will be recorded in the eCRF from the time of first dose through 30 days after the last dose of SRF617, 30 days after the last dose of etrumadenant, or 90 days after the last dose of zimberelimab (30 days after the last dose of zimberelimab if the patient starts another anticancer therapy), whichever is later. An AE will be followed until it is either resolved, has returned to Baseline, or is determined to be a stable or chronic condition. All SAEs occurring from the signing of the ICF through 30 days after the last dose of SRF617, 30 days after the last dose of etrumadenant, or 90 days after the last dose of zimberelimab (30 days after the last dose of zimberelimab if the patient starts another anticancer therapy), whichever is later, will be processed as outlined in Section 8.2.2.

At each required visit during the trial, all AEs that have occurred since the previous visit must be reviewed by the Investigator. The Investigator must determine if the AE is serious or nonserious.

The Investigator must assign the following AE attributes:

- AE diagnosis or syndrome(s) if known
  - If not known at time of the report, record the signs and/or symptoms as AEs and provide an updated report with diagnosis when obtained.
- Dates of onset and resolution
- Severity as defined per protocol
- Assessment of relatedness to each study drug
- Action taken with each study drug as a result of the AE

In general, an AE that is the primary cause of subsequent events should be identified by the primary cause; eg, for dehydration due to diarrhea, the AE would be diarrhea. However, AEs occurring secondary to an initiating event that are separated in time should be recorded as independent events; eg, for sepsis secondary to pneumonia, both events should be recorded.

The signs and symptoms of progressive disease that meet the AE criteria should be reported as specific AEs and not as disease progression.

